090177e1848ce2dd\Approved\Approved On: 23-Sep-2013 15:48

were observed following 12 weeks of dosing with ertugliflozin. There was a suggestion of changes in markers of bone resorption, though there did not appear to be a clear dose-dependent effect with increasing dose of ertugliflozin. In totality, the clinical relevance of these findings remains unclear. However, the effect of ertugliflozin on BMD will be evaluated in this trial, and all clinical fractures will be adjudicated throughout the Phase 3 program by an independent committee and will be included in a pooled analysis.

In the clinical program to date, no clinically significant changes from baseline in serum aminotransferases (ALT and AST) have been observed.

Phase 3 clinical trial data from another SGLT2 inhibitor, dapagliflozin, revealed a numerical imbalance in the rates of breast and bladder cancer in dapagliflozin-treated subjects compared to control.¹¹ The causal relationship to dapagliflozin for this finding is uncertain given the small number of events and the absence of any preclinical signal (ie, no reported increase in either tumor in carcinogenicity studies) with dapagliflozin. Moreover, in the larger clinical program of another SGLT2 inhibitor, canagliflozin, no cancer imbalance, including in breast or bladder cancer events, was reported. Because thorough evaluation of malignancies is important in the development program of all investigational medications, detailed information will be collected for subjects who develop a malignancy. This information could include but is not limited to relevant medical history, biopsy, or operative reports, etc.

Complete information for this compound may be found in the Single Reference Safety Document (SRSD), which for this study is the Investigators' Brochure for ertugliflozin (PF-04971729).

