7.8.2. Fractures

Spontaneously reported fractures will be adjudicated by an independent and blinded external fracture adjudication committee (FAC) comprised of radiologists. In the event that a subject experiences a clinical fracture during the trial, the radiographs and/or local radiologist report and other relevant documentation will be sent to the FAC. The FAC will review the radiograph(s) (if available) and, where applicable the local radiologist report and other source documents and confirm the presence of the fracture, location of fracture, number of fractures, and type of fracture (ie, high-trauma, low-trauma, pathological fracture, stress fracture, and other fracture). The FAC members will not be Investigators or sub-Investigators in any trial in the Phase 3 program and they will be blinded to the subject's assigned treatment group. A FAC charter will describe the precise mandates and procedures to be used for the adjudication of clinical fractures.

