9.1. Sample Size Determination

With respect to the primary endpoint of reduction in HbA1c from Baseline to Week 26 and assuming an SD of 1.0%,¹¹ the sample size of approximately 600 subjects (200 per arm) provides at least 99% power to detect a difference of 0.5% between each ertugliflozin dose and placebo (and 98% power for detecting this difference for both doses vs placebo) using a two-sided 0.05 alpha level test, allowing for a dropout rate of up to 20%. To control the overall Type I error rate at 0.05 a sequential testing approach will be used across the primary and secondary efficacy endpoints for which hypotheses will be tested, and for the two doses of ertugliflozin.

090177e1848ce2dd\Approved\Approved On: 23-Sep-2013 15:48

The sample size for this trial also provides adequate precision for the comparisons of ertugliflozin versus placebo with respect to the changes in BMD from Baseline to Week 26. In a recent study of another SGLT2 inhibitor (dapagliflozin) in subjects with inadequately controlled T2DM on metformin, the largest variability for the change from baseline in BMD was at the total hip site, with a standard deviation (SD) of approximately 3.3% after 50 weeks.¹³ Assuming that the SD of the change in BMD increases over time, 3.3% was taken as a conservative estimate of the variability at 26 weeks for precision calculations and also to ensure adequate precision for all BMD sites.

Assuming an SD of 3.3% and allowing for a dropout rate of up to 15% at Week 26, the half-width of the 95% confidence interval for the between-treatment difference is expected to be $\pm 0.7\%$ from the point estimate for the overall study population, and also of approximately $\pm 1.0\%$ for the post-menopausal for ≥ 3 years sub-group which will be analyzed separately (approximately 50% of the overall study population). These CI half-widths would be precise enough to rule out clinically relevant changes in BMD, both for the overall study population and the ≥ 3 years post-menopausal subgroup. This is based on changes in BMD that are approximately 50% of the average changes from baseline to Week 80 observed for thiazolidinediones, which are known to be associated with significant bone loss and an increased risk of fracture.¹⁹

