9.3. Safety Analysis

The safety analysis population will consist of all treated subjects, ie, all subjects who received at least one dose of investigational product.

The Medical Dictionary for Regulatory Activities (MedDRA) will be used to classify all adverse events (AEs) with respect to system organ class and preferred term. Summaries of AEs will include treatment-emergent AEs according to treatment group.

To avoid the confounding influence of rescue therapy, the primary approach for most safety analyses will exclude data from the period following the initiation of rescue therapy. A secondary approach will include data following the initiation of rescue therapy. For serious AEs and discontinuations due to AEs, the approach that includes data following the initiation of rescue therapy will be considered primary.

Descriptive statistics will be used to summarize results and changes from baseline in clinical laboratory tests and in vital signs. The number and percentage of subjects with abnormal findings from ECGs will be tabulated by treatment group.

Furthermore, a 3-tier approach will be used to summarize AEs. Tier-1 consists of pre-specified adverse events of interest, and will include AEs or collections of AEs related to urinary tract infection, genital mycotic infection, hypoglycemia and hypovolemia. Where available, standard MedDRA queries will be used to pool different AE terms that are related to the Tier-1 AEs. The precise AE terms that will contribute to the Tier-1 endpoints will be

090177e1848ce2dd\Approved\Approved On: 23-Sep-2013 15:48

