determined prior to unblinding. For these events, the percentage of subjects with incident AE, the risk difference, its 95% confidence interval, and p-value will be provided. The confidence intervals and p-values are not adjusted for multiplicity and are provided for screening purposes only. Tier-2 AEs are those that are not Tier-1, but are common, occurring in at least 4 subjects in any treatment arm. The cut-off of at least 4 events was chosen because the 95% confidence interval for the between-group difference in percent incidence will always include zero when treatment groups of equal size each have less than 4 events and so adds little to the interpretation of potentially meaningful differences. For these events, the percentage of subjects with incident AE, the risk difference and its 95% confidence interval will be provided. The confidence intervals are for estimation purposes only. Tier-3 AEs are all other AEs (neither Tier-1 nor Tier-2). For Tier-3 AEs, only within-group incidence proportions will be tabulated.

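### Section 9.3 plans no pooled between-arm estimate for adjudicated fractures, and a cut-off based on intervals including zero can withhold the upper bound that a reader of a rare harm needs

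*Combined protocol and SAP*

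**What the plan says.** Section 9.3 sorts AEs into three tiers. Tier-1 is pre-specified and "will include AEs or collections of AEs related to urinary tract infection, genital mycotic infection, hypoglycemia and hypovolemia". Standard MedDRA queries are to be used, where available, to pool terms for these groups; the section does not describe pooling for any other event. Tier-2 holds other AEs "occurring in at least 4 subjects in any treatment arm", and for these "the risk difference and its 95% confidence interval will be provided". For everything else: "For Tier-3 AEs, only within-group incidence proportions will be tabulated". The reason given for the cut-off is that the interval "will always include zero when treatment groups of equal size each have less than 4 events and so adds little to the interpretation".

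Fracture is handled elsewhere. Section 7.8.2 states: "Spontaneously reported fractures will be adjudicated by an independent and blinded external fracture adjudication committee (FAC) comprised of radiologists". That committee confirms each fracture and records its site, number and type, including whether it was low-trauma. Section 1.4 adds that "all clinical fractures will be adjudicated throughout the Phase 3 program by an independent committee and will be included in a pooled analysis". Section 9 contains no analysis of the adjudicated fractures for this trial.

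**The concern.** Whether an interval includes zero is a significance criterion. For a rare harm the useful quantity is the largest excess still compatible with the data, and an interval that includes zero supplies it. The plan reasons this way for bone density: Section 9.1 defends the sample size because the BMD intervals would be narrow enough to rule out a relevant change, and it sets the benchmark by reference to drugs linked to fracture. Section 9.3 does not carry that reasoning over to fracture itself.

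Bone safety is one of the trial's stated purposes, about half the sample is to be women at least 3 years post-menopausal, and a blinded committee adjudicates every reported fracture. The data will exist. Yet if fracture falls below the cut-off, the trial's report would give fracture proportions by arm and no statement of how large a difference remains possible.

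**Working it through.** **Inputs.** About 200 subjects per arm (Section 9.1: "the sample size of approximately 600 subjects (200 per arm"), allocated 1:1:1 (Section 5.1). Two-sided 95% intervals, z = 1.96; Section 9.3 names no method. Tier-2 cut-off: 4 subjects in any arm (Section 9.3). The documents give no fracture rate, so all fracture counts and rates below are assumptions.

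**Formulas,** for a/n vs b/m:
- Wald: d ± 1.96 × √[p₁(1−p₁)/n + p₂(1−p₂)/m], where d = a/n − b/m.
- Miettinen-Nurminen (MN): all δ with |d − δ| ≤ 1.96 × √{[p̃₁(1−p̃₁)/n + p̃₂(1−p̃₂)/m] × (n+m)/(n+m−1)}, where p̃₁ and p̃₂ are the maximum-likelihood rates given p₁ − p₂ = δ.
- Newcombe: combines the two Wilson intervals.

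**Step 1: the plan's own claim.** The extreme case below the cut-off is 3 vs 0. Wald: 0.015 ± 1.96 × √(0.015 × 0.985/200) = 0.015 ± 0.0168, that is −0.18 to 3.18 points. Newcombe gives −0.63 to 4.32 and MN −0.40 to 4.32. All pairs with 0 to 3 events per arm were checked at 200 and at 160 per arm. None excludes zero by any of the three methods, so the claim is reproduced.

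**Step 2: what is withheld.** For 0 vs 0 the MN upper bound has a closed form: 1.96²/(200 × 399/400 + 1.96²) = 3.84/203.34 = 1.89 points. The full set (MN, 200 per arm):

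| Events, dose vs control | Upper bound, points |
|---|---|
| 0 vs 0 | 1.89 |
| 1 vs 0 | 2.78 |
| 2 vs 0 | 3.58 |
| 3 vs 0 | 4.32 |
| 3 vs 1 | 3.88 |
| 3 vs 3 | 3.00 |

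**Step 3: splitting by term.** Section 9.3 classifies AEs by system organ class and preferred term but does not say at which level the 4 subjects are counted. Suppose it is by preferred term, and that fractures at different sites carry different terms. Six subjects with a fracture on one dose, split 3 + 2 + 1 over three terms, against none on control, give three Tier-3 rows and no interval. Pooled:

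| Events, dose vs control | MN 95% CI, points | Newcombe 95% CI, points |
|---|---|---|
| 4 vs 0 | 0.09 to 5.03 | −0.24 to 5.03 |
| 5 vs 0 | 0.59 to 5.72 | 0.14 to 5.72 |
| 6 vs 0 | 1.08 to 6.40 | 0.52 to 6.39 |
| 6 vs 1 | −0.10 to 5.96 | −0.29 to 5.91 |
| 7 vs 1 | 0.33 to 6.61 | 0.10 to 6.57 |
| 8 vs 2 | −0.08 to 6.82 | −0.23 to 6.76 |

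For 4 vs 0, Fisher's exact p is 0.12. A pooled difference therefore excludes zero by both methods only when the imbalance is marked.

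**Step 4: if all fractures count as one event.** No comparison is made when all three arms have 3 or fewer. With F(p) = P(X ≤ 3) for X binomial(200, p): F(0) = 1, F(0.005) = 0.981, F(0.01) = 0.858, F(0.015) = 0.647, F(0.02) = 0.432. The chance is F(dose) × F(control)² if one dose is affected and F(dose)² × F(control) if both are.

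| Assumed rate, dose vs control | One dose affected | Both doses affected |
|---|---|---|
| 1% vs 0% | 86% | 74% |
| 1.5% vs 0.5% | 62% | 41% |
| 2% vs 0.5% | 42% | 18% |

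These rates are illustrative and carry no time horizon; counts at 26 and 104 weeks would differ.

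**The case against.** The strongest reply is that the trial answers its bone question through BMD. Its stated bone endpoints are BMD and biomarkers, not fracture, and Section 9.2.3.1 gives BMD between-arm estimates with 95% CIs, including a separate analysis in the post-menopausal women. Fracture inference is placed at program level, which is defensible for a rare event. Tier-3 still shows incidence by arm, so a reader can compute an interval for any tabulated term. An external monitoring committee reviews safety throughout, with all serious events seen unblinded. Section 9 also defers detailed methods to a statistical analysis plan whose separate text is not in the document supplied and which may already cover this. All of this stands, and it limits the weight of the point. It does not supply a pooled fracture estimate for this trial, whose Phase A report is written on its own (Section 9.4). Rows split by term also do not give a reader the number of subjects with any fracture.

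Three stronger readings are tempting and not supported:
- That the cut-off is a numerical error. Step 1 shows that it is not.
- That the plan leaves fracture with no upper bound. The counting level is not fixed, and any single fracture term reaching 4 subjects in an arm gets its own interval.
- That four fractures against none would already contradict the cut-off's rationale. This holds by Wald and MN but not by Newcombe, and Section 9.3 names no method.

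**Conclusion.** The point holds in limited form. The cut-off is arithmetically sound, but the inference that an interval including zero adds little does not suit a rare harm: at 200 per arm the withheld upper bounds are about 1.9 to 4.3 points for counts from 0 vs 0 to 3 vs 0. Section 9 has no pre-specified pooled contrast of adjudicated fractures for this trial. Under a preferred-term count, a marked imbalance such as 6 vs 0 could go without an interval. Under a single-group count, the chance of no comparison ranges from 18% to 86% over the assumed rates. The conclusion rests on the text of Section 9 as supplied. The primary and BMD analyses are unaffected. This is a cheap improvement to the safety reporting.

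**What to change.** In Section 9.3, or in the statistical analysis plan, add committee-confirmed clinical fracture as a pre-specified event, with all sites counted as one group and low-trauma fractures also shown. Give the risk difference and 95% CI by Miettinen-Nurminen for each dose versus the control arm, whatever the count, and say that the upper bound is the figure to read.

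Two details need stating. Report Phase A and the whole trial separately, because control subjects may receive blinded glimepiride in Phase B (Section 5.3.5.1). Include fractures after glycemic rescue, as is done for BMD, since the default in Section 9.3 for most safety analyses is to exclude post-rescue data. The general cut-off wording can stay for other AEs.

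The cost is a sentence or two and a few table rows; fractures are already collected and adjudicated. The downside is some wide, unadjusted intervals, to be labelled as for estimation only, as Section 9.3 already does for Tier-2.

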9.4. Planned Analyses

The results of Phase A will be analyzed, and a clinical study report for Phase A will be written while Phase B is on-going. The results of Phase A will not be used to make any changes to the design or conduct of Phase B. An unblinding plan will be developed and put into place in order to limit the extent of sponsor unblinding that takes place during the reporting of Phase A and to ensure that sponsor staff who interact with clinical sites do not have access to treatment assignments during Phase B.

No formal interim analyses are planned (other than in support of the independent DMC regular review of safety), but may be conducted if necessary in support of Regulatory filings or requests.

9.5. Data Monitoring Committee

This trial will use an external Data Monitoring Committee (E-DMC).

The E-DMC will be responsible for ongoing monitoring of the safety of subjects in the trial and a separate E-DMC Charter will describe the precise mandates of the E-DMC. The recommendations made by the E-DMC to alter the conduct of the trial will be forwarded to the Sponsor for final decision. The E-DMC charter will specify the role and responsibilities of the E-DMC and also the contact individuals within the Sponsor organization and the E-DMC responsible for communications between these organizations. The Sponsor will forward such decisions, which may include summaries of aggregate analyses of endpoint events and of safety data which are not endpoints, to regulatory authorities, as appropriate.

10. QUALITY CONTROL AND QUALITY ASSURANCE

During study conduct, Pfizer/Merck or their agents will conduct periodic monitoring visits to ensure that the protocol and Good Clinical Practices (GCPs) are being followed. The monitors may review source documents to confirm that the data recorded on CRFs is accurate. The Investigator and institution will allow Pfizer/Merck monitors/auditors or its agents and appropriate regulatory authorities direct access to source documents to perform this verification.

090177e1848ce2dd\Approved\Approved On: 23-Sep-2013 15:48

The study site may be subject to review by the Institutional Review Board (IRB)/Independent Ethics Committee (IEC), and/or to quality assurance audits performed by Pfizer, or companies working with or on behalf of Pfizer, and/or to inspection by appropriate regulatory authorities.

It is important that the Investigator(s) and their relevant personnel are available during the monitoring visits and possible audits or inspections and that sufficient time is devoted to the process.

11. DATA HANDLING AND RECORD KEEPING

11.1. Case Report Forms/Electronic Data Record

As used in this protocol, the term CRF should be understood to refer to either a paper form or an electronic data record or both, depending on the data collection method used in this trial.

A CRF is required and should be completed for each included subject. The completed original CRFs are the sole property of Pfizer/Merck and should not be made available in any form to third parties, except for authorized representatives of Pfizer/Merck or appropriate regulatory authorities, without written permission from Pfizer/Merck.

The Investigator has ultimate responsibility for the collection and reporting of all clinical, safety and laboratory data entered on the CRFs and any other data collection forms (source documents) and ensuring that they are accurate, authentic / original, attributable, complete, consistent, legible, timely (contemporaneous), enduring and available when required. The CRFs must be signed by the Investigator or by an authorized staff member to attest that the data contained on the CRFs is true. Any corrections to entries made in the CRFs, source documents must be dated, initialed and explained (if necessary) and should not obscure the original entry.

In most cases, the source documents are the hospital's or the physician's subject chart. In these cases data collected on the CRFs must match the data in those charts.

In some cases, the CRF, or part of the CRF, may also serve as source documents. In these cases, a document should be available at the Investigator's site as well as at the Sponsor and clearly identify those data that will be recorded in the CRF, and for which the CRF will stand as the source document.

11.2. Record Retention

To enable evaluations and/or audits from regulatory authorities or Pfizer/Merck, the Investigator agrees to keep records, including the identity of all participating subjects (sufficient information to link records, eg, CRFs and hospital records), all original signed informed consent documents, copies of all CRFs, safety reporting forms, source documents, and detailed records of treatment disposition, and adequate documentation of relevant correspondence (eg, letters, meeting minutes, telephone calls reports). The records should be retained by the Investigator according to International Conference on Harmonisation (ICH),

090177e1848ce2dd\Approved\Approved On: 23-Sep-2013 15:48

local regulations, or as specified in the Clinical Study Agreement (CSA), whichever is longer.

If the Investigator becomes unable for any reason to continue to retain study records for the required period (eg, retirement, relocation), Pfizer should be prospectively notified. The study records must be transferred to a designee acceptable to Pfizer, such as another Investigator, another institution, or to an independent third party arranged by Pfizer. Investigator records must be kept for a minimum of 15 years after completion or discontinuation of the trial or for longer if required by applicable local regulations.

The Investigator must obtain Pfizer's written permission before disposing of any records, even if retention requirements have been met.

12. ETHICS

12.1. Institutional Review Board (IRB)/Independent Ethics Committee (IEC)

It is the responsibility of the Investigator to have prospective approval of the study protocol, protocol amendments, informed consent documents, and other relevant documents, eg, recruitment advertisements, if applicable, from the IRB/IEC. All correspondence with the IRB/IEC should be retained in the Investigator File. Copies of IRB/IEC approvals should be forwarded to Pfizer or its designee.

The only circumstance in which an amendment may be initiated prior to IRB/IEC approval is where the change is necessary to eliminate apparent immediate hazards to the subjects. In that event, the Investigator must notify the IRB/IEC and Pfizer in writing immediately after the implementation.

12.2. Ethical Conduct of the Study

The study will be conducted in accordance with legal and regulatory requirements, as well as the general principles set forth in the International Ethical Guidelines for Biomedical Research Involving Human Subjects (Council for International Organizations of Medical Sciences 2002), Guidelines for GCP (ICH 1996), and the Declaration of Helsinki (World Medical Association 1996 & 2008).

In addition, the study will be conducted in accordance with the protocol, the ICH guideline on GCP, and applicable local regulatory requirements and laws.

12.3. Subject Information and Consent

All parties will ensure protection of subject personal data and will not include subject names on any sponsor forms, reports, publications, or in any other disclosures, except where required by laws.

Subject names, address, birth date and other identifiable data will be replaced by a numerical code consisting of a numbering system provided by Pfizer in order to de-identify the trial subject. In case of data transfer, Pfizer/Merck will maintain high standards of confidentiality and protection of subject personal data.

090177e1848ce2dd\Approved\Approved On: 23-Sep-2013 15:48

The informed consent document must be in compliance with ICH GCP, local regulatory requirements, and legal requirements.

The informed consent document(s) used during the informed consent process must be reviewed by the sponsor, approved by the IRB/IEC before use, and available for inspection.

The Investigator must ensure that each study subject, or his/her legal representative, is fully informed about the nature and objectives of the trial and possible risks associated with participation. The Investigator, or a person designated by the Investigator, will obtain written informed consent from each subject or the subject's legal representative before any study-specific activity is performed. The Investigator will retain the original of each subject's signed consent document.

